## V. Experimental Design and Methods:

- i) Provide concise description of experimental design and procedures to be used to accomplish study goals. Include precise descriptions of all tests and measurements, and their expected duration. Include optional testing and blinding/un-blinding procedures if applicable.

Research Design: A cluster randomized control trial will be used to test hypotheses. The NM Department of Health, Office of School and Adolescent Health provided a list of recommendations for schools with functioning SBHCs serving a large Hispanic student population. PI [name] successfully approached these schools about collaborating on the proposed research; they agreed (see Letters of Support). To limit the possibility of confounding effects, our collaborating high schools all share the following four characteristics: 1)

Enrollment/ethnicity: At least >700 enrolled students, with at least 40% Hispanic youth, 2) Environmental resources: at least one outdoor field, one gymnasium, and physical activity opportunities, 3) Food service resources: at least one cafeteria, competitive foods (foods brought into schools from outside vendors), and vending machines, and 4) a functioning SBHC. To further control for plausible alternative explanations of outcomes between groups, pretest differences will be compared between groups. The pretests will allow exploration of the possible size and direction of bias that may exist. Thus, the joint use of a pretest and a comparison group will allow examination of possible threats to validity (see Analyses). Assessments will be conducted at pretest (baseline) and annually for two more years (see Table 1). The assessment time waves will allow us to follow 9th grade students annually until their 11th grade year and 10th grade students until their 12th grade year.

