Data Collection Measurements: All measures will be collected in both intervention and comparison schools. Protocols with standardized procedures and quality control procedures will be followed by research staff to ensure accuracy, precision, and completeness of data collection. Training for data collection team members will be given by [name], MS (for physical activity related measures) and by [name] (for anthropometrics and nutrition related measures). Each year, before measurements begin, these investigators will retrain and certify the data collection team in all measures. Demographic, physical, dietary intake and physical activity data will

be collected at baseline (pretest), at one year (intermediate), and at 2 years (follow-up) in both intervention and comparison schools. These time intervals will allow us to assess pretest to posttest changes on hypothesized outcomes, and intermediate effects of the intervention. Students will be reimbursed \$20 per measurement wave (total possible=\$60); compensation is consistent with other clinical trials in NM.

- Demographic information to be collected on participants and their parents include age, sex, socioeconomic status, education, and race/ethnicity, using our previously developed Health History Survey. Our Health History Survey also includes questions on family history of type 2 diabetes (first and second degree relatives), chronic medical conditions, and current medications.

A follow-up health history will be administered at intermediate (year one) and follow-up (year two) measurement periods. Participants will update contact and health information. Participants will be excluded at intermediate and follow-up measurement periods if they are pregnant or have been diagnosed with an eating disorder.

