- Analysis of intervention effects: Analyses will be conducted in a multilevel framework to account for clustering within schools. Mixed effects linear regression (SAS Proc Mixed) will be utilized for continuous outcomes (e.g., minutes of moderate or vigorous physical activity, BMI z score) and the generalized estimating equation approach (SAS Proc Genmod) will be used for binary dependent variables (e.g., hypertriglyceridemia, prediabetes defined by glucose and hemoglobin A1c) to study intervention impact on physical, behavioral and biochemical outcomes after 2 years. The following main outcomes of interest will be assessed: (**Hypothesis 1a**) Incidence of overweight and obesity after 2 years among students who were not overweight or obese at baseline; (**Hypothesis 1b**) sweetened beverage consumption, fat intake, fruits and vegetable intake, whole grain consumption, and time in moderate and vigorous physical activity after 2 years; (**Hypothesis 2**) BMI z score and HOMA-IR (insulin resistance index score) after 2 years among those students who were overweight or obese at baseline. Additional outcomes that will be assessed in the cohort of students who are overweight or obese at baseline include waist circumference, percent body fat, blood pressure percentiles, and biochemistries (glucose, insulin, hemoglobin A1c, and lipids) after 2 years. Hypotheses will be tested at a 0.05 significance level, two sided. Descriptive statistics (e.g., means  $\pm$  SD, percentages) will be used to evaluate process data. Bivariate relationships of participants' BMI z score change to student attendance will be assessed in the intervention group and a multivariate analysis will be subsequently used to control for other demographic variables. An intention to treat analysis plan will be used. To that end, adolescents who complete a fraction of the sessions will still be accounted for in the analyses. Data imputation methods will be used for missing data. Additionally, we will assess number of sessions completed to determine how attendance is associated with outcomes. The study will assess BMI trends in NM using data from the Youth Risk Resiliency Survey (the NM version of the CDC's Youth Risk Behavior Survey) to evaluate secular trends. The study will use the school's demographic data on race/ethnicity, age, and free/reduced lunch meals to assess the representativeness of the recruited population. If the recruited population does not appear to be representative, we will use weighted data

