
analysis procedures to estimate outcomes for the school population.

Baseline values will be included as covariates in the mixed effects linear regression models for continuous dependent variables and the generalized estimating equation models for binary dependent values including the incidence of overweight or obesity or the presence or absence of specific components of the metabolic syndrome. For students who repeat grades, we will include "repeated grade" as a covariate. Intervention (coded 0=control and 1=intervention) will be entered as a fixed effect into the multilevel models predicting outcomes. One equation will be estimated for each of the outcomes of interest. This approach is conceptually identical to an analysis of variance or covariance (ANOVA or ANCOVA) but has two distinct advantages. First, it allows for the analysis of clustered data, and second, it avoids list-wise deletion of subjects with missing assessments. The model relaxes the restrictive assumption that the data are missing completely at random and provides unbiased estimates under the less restrictive assumption of missing at random. This approach to missing data, i.e., the use of techniques that include full information maximum likelihood estimation of missing values, will be used.

• **Analysis of semi-structured Interviews (Aim 3):** Parent and student interviews conducted following the intervention will be analyzed using standard qualitative assessment methods. [name] will lead this analytic process. The interviews will each be transcribed and distributed to the research team. Each member will review transcripts independently, identifying themes related to the stem questions as well as other emergent areas of interest. The analysis will proceed in an iterative fashion, with the team reviewing sets of 3 to 4 transcripts in each category (parent and student). Following the independent reading, the team will meet to list the full range of themes, identify anomalous or unanticipated findings, and revise the interview guides accordingly. This process will continue until the team has reached consensus. At that stage, the thematic list will be converted into a template for coding purposes. Interviews will be coded in NVivo 9 (Melbourne, Australia), a qualitative data analysis software package, at which point queries to refine analytic and interpretive understandings will be conducted.

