## VI. Human Subjects:

i) Describe characteristics (inclusion criteria) of subject population, including precautions to be taken with vulnerable populations (e.g. children, prisoners, mentally ill/disabled person). Answer for each subject group, if different.

Inclusion criteria are as follows: 1) enrolled in 9th or 10th grade at the participating school, and 2)

informed written assent and informed written parent/guardian consent to participate in the full study for two years.

Research nurses or phlebotomist and clinical providers who are familiar with working with children and adolescents are used to collect data in this study. Data collection will be done in a private setting. Parental consent and adolescent assent is required prior to participation.

ii) Provide approximate number of subjects (both control and intervention groups).

A total of 960 high school students in the 9th and 10th grades (ages 14-17 years) will be recruited from 8 high schools to participate (480 in the intervention group and 480 in the comparison group); students will be followed until they are in the 11th and 12th grades, respectively. Enrollment will end when samples are met.

Due to higher than anticipated attrition at the high schools from baseline to 1st annual measurements, we will increase our current total sample enrollment (n=960) by 5%, to give a new total sample of 1008 participants.

iii) What characteristics (exclusion criteria) would exclude subjects, who are otherwise eligible, from this study? (Answer for each subject group, if different.)

Exclusion criteria are as follows: 1) blood pressure in the range of stage 2 hypertension in which an immediate medical assessment for pharmacotherapy is required, 2) diabetes, 3) use of oral or injectable corticosteroids or antipsychotics, 4) inability to perform moderate to vigorous physical activity, 5) not ambulatory, 6) medications for the control of diabetes, hypertension, and hyperlipidemia (or high cholesterol), 7) a score of 20 or more on the EAT-26 screening measure, and 8) developmental disorders that affect weight or the ability to understand the study procedures or counseling.

Students who meet withdrawal criteria (e.g., pregnancy) will be offered care in the SBHC.

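### The only planned model for each outcome adjusts for grade repetition, which probably occurs after schools are allocated, so the arm effect may not be the promised intention-to-treat effect

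*Combined protocol and SAP*

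**What the plan says.** All of this is in the combined protocol and SAP.

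- Section V.i, Research Design: "A cluster randomized control trial will be used to test hypotheses". "Assessments will be conducted at pretest (baseline) and annually for two more years". Ninth graders are expected to be in 11th grade at the end, and 10th graders in 12th.
- Section V.iii, Analysis of intervention effects: "An intention to treat analysis plan will be used". The models include baseline values as covariates. The next sentence reads: "For students who repeat grades, we will include 'repeated grade' as a covariate". Then: "Intervention (coded 0=control and 1=intervention) will be entered as a fixed effect into the multilevel models predicting outcomes". One equation is planned per outcome, so no version without the covariate is promised.
- Section V.i, Data Collection Measurements: "Demographic information to be collected on participants and their parents include age, sex, socioeconomic status, education, and race/ethnicity". Earlier grade repetition is not among the named items.

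No section defines when grade repetition is measured, and none gives its expected frequency.

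**The concern.** A randomised comparison is protected only for variables fixed before allocation. If the intervention can change whether a student repeats a grade, adjusting for repetition does two things. It removes any part of the effect that runs through repetition. It also opens a non-randomised path between arm and outcome through unmeasured causes of both repetition and weight change, such as engagement with school.

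A route from intervention to repetition is more plausible for students at or above the 85th BMI percentile. They are offered 16 clinician sessions at school over two years, in a style meant to build autonomy and self-efficacy. It is less plausible for students below the 85th percentile, who get a discussion each year. So Hypothesis 2, and Hypothesis 1b in the heavier group, are more exposed than Hypothesis 1a.

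Because each outcome has a single model, the reported effect would carry the adjustment with nothing beside it for comparison.

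**Working it through.** **1. Timing, from the text.** Three features point to repetition during follow-up: the covariate is listed apart from baseline values, prior repetition is not a named baseline item, and students are expected to advance two grades under observation. One feature leaves room for doubt: section VI.ii enrols 9th and 10th graders aged 14–17, a range that could include students already repeating at entry. The date of school randomisation is not given. Post-allocation timing is therefore an inference.

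**2. Do the plan's own figures depend on the covariate?** Inputs from Sample size and power analysis: 8 schools, ICC 0.01, two-sided alpha 0.05, power 0.80, and 400 or 224 students after attrition. Design effect = 1 + (m - 1) × ICC; noncentral t on 8 - 2 = 6 df.

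- Below the 85th percentile: m = 50; 1 + 49 × 0.01 = 1.49; 200/1.49 = 134.2 effective per arm; detectable effect 0.411 (stated 0.41).
- At or above the 85th: m = 28; 1 + 27 × 0.01 = 1.27; 112/1.27 = 88.2 per arm; detectable effect 0.507 (stated 0.51).

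Both reproduce, and grade repetition enters neither.

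**3. Size of the shift in a linear model.** With b the coefficient of repetition in the adjusted model and p0, p1 the repeat rates in comparison and intervention schools:

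adjusted arm effect - unadjusted arm effect = b × (p0 - p1).

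If p0 = p1, the shift is zero whatever b is. Every rate and b below is an assumption.

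*Narrow scenarios.* An unmeasured factor raises the log-odds of repeating by 1.0 per SD and BMI z by 0.10–0.15 per SD, and the intervention lowers repetition. This gives p0 about 17%, p1 about 11–15% and b about 0.09–0.13 z. The true effect is set at -0.16.

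- Smallest: 0.09 × (0.17 - 0.15) = 0.0018; adjusted effect -0.158; attenuation 0.0018/0.16 = 1%.
- Largest: 0.13 × (0.17 - 0.11) = 0.0078; adjusted effect -0.152; attenuation 0.0078/0.16 = 5%.

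*Wider scenarios, in SD units.* Comparison rate 5–20%; intervention rate equal, 20% lower or 50% lower; correlation of repetition with the unmeasured cause 0.3 or 0.6; that cause worth 0.3 SD of outcome; direct effect of repeating 0 or 0.3 SD. The extremes both arise at 20% versus 10%.

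- b about -0.33: -0.33 × 0.10 = -0.033 SD.
- b about +0.14: 0.14 × 0.10 = +0.014 SD.

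The sign depends on whether repeaters do better or worse on the outcome.

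**4. Scale against Hypothesis 2.** The plan gives no SD for BMI z change. Power of 84% at 0.16 with 88.2 effective students per arm implies an SD of about 0.30 (t, 6 df) to 0.36 (normal).

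- 0.033 × 0.30 = 0.010 and 0.033 × 0.36 = 0.012 z, or 6–7% of 0.16.
- The implied standard error is 0.16/(1.960 + 0.994) = 0.054 (normal), or 0.30 × √(2/88.2) = 0.045 (t). The narrow shifts of 0.002–0.008 z are 0.002/0.054 = 4% to 0.008/0.045 = 18% of one standard error.

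The identity in step 3 is for linear models. The link for the binary incidence model is not stated, and no separate size was worked out for Hypothesis 1a.

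**The case against.** The strongest reply has four parts.

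- **Timing is not stated.** If the variable means repetition before schools were allocated, it is an ordinary baseline covariate and the objection falls. This stands as a limit on confidence, but not as a defence of the present wording, which leaves the covariate undefined in the only planned model.
- **Even within follow-up, some repeats may precede treatment.** The first weight-management meeting is booked for after the summer, so repetition of the entry grade might be settled before any ACTION session. Yet the screening visit is also described as a start-of-year visit, so the documents do not settle this.
- **Nothing in the documents says the intervention alters repetition.** If it does not, there is no bias, and adjustment may gain some precision and correct chance imbalance among eight schools. This stands. A claim that the covariate has no benefit would be too strong.
- **The size is small on any assumption tried.** This also stands.

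A reader might go further and infer that Hypotheses 1a, 1b and 2 all cease to estimate the intention-to-treat effect. The documents do not support that: the 16 sessions apply only to the heavier group, and the departure depends on a difference in repeat rates by arm that nobody has reported. A reader might also infer that repeat status would be unknown for students who leave school; no section says so.

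**Conclusion.** The point holds in conditional form. As written, the single model for each outcome probably conditions on an event after allocation, which sits badly with the plan's intention-to-treat commitment. The arm coefficient may differ from the intention-to-treat effect if two things are true: repetition is counted during follow-up, and its rate differs by arm because of the intervention.

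Under assumed rates the shift is about 1–5% of a 0.16 BMI z effect, or -0.033 to +0.014 SD in the wider scenarios. It can go either way, and in the linear models it is nil at equal rates. It would not be right to infer that the power statements are wrong, since 0.41 and 0.51 reproduce without reference to this covariate. Severity is minor and confidence moderate, the main uncertainty being the unstated timing.

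**What to change.** In Analysis of intervention effects, replace the sentence on repeated grade with wording to this effect: grade repetition after school allocation is not a covariate in the primary or secondary models; it is tabulated by arm; and a model including it is reported only as a labelled sensitivity analysis. Grade at enrolment (9th or 10th), known for every student through eligibility, may be added as an optional baseline covariate. It is not needed for validity.

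If the sponsor means repetition before entry, the plan should define it so and take the value from baseline records.

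The cost is one or two sentences, with no change to visits, sample size or stated power. The possible downside is a small loss of precision if repetition predicts outcome and is unaffected by arm.

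### The Proc Mixed model for H2 and H1b, as most naturally read, has one year-2 response per student, so it does not by itself avoid list-wise deletion, and the plan gives the year-1 values no role in it

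*Combined protocol and SAP*

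**What the plan says.** The model is described in section V.iii under Analysis of intervention effects. "Mixed effects linear regression (SAS Proc Mixed) will be utilized for continuous outcomes", and the only clustering level named is the school: "Analyses will be conducted in a multilevel framework to account for clustering within schools". The H2 outcomes are "BMI z score and HOMA-IR (insulin resistance index score) after 2 years among those students who were overweight or obese at baseline", and the H1b outcomes are likewise defined after two years. "Baseline values will be included as covariates in the mixed effects linear regression models for continuous dependent variables". Intervention enters as a single 0/1 fixed effect, and "One equation will be estimated for each of the outcomes of interest". The plan likens the approach to ANOVA or ANCOVA and claims as an advantage that "it avoids list-wise deletion of subjects with missing assessments", with unbiased estimates under missing at random.

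The same section commits, in one sentence, to imputing missing data, and later to techniques that include full information maximum likelihood. It does not say which applies to which hypothesis, or which variables enter. Under Data Collection Measurements (section V.i), the assessment times are said to allow study of change from pretest to posttest "and intermediate effects of the intervention". The analysis section contains no year-1 analysis.

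**The concern.** A likelihood-based mixed model recovers information from incomplete students only through their other responses. If each student has one response, at year 2, Proc Mixed omits the record when that value is missing. No wave term, arm-by-wave term, student-level random effect or within-student covariance is stated, so the model described lacks the property claimed for it.

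The validity of the H2 and H1b estimates is at stake. Students whose BMI z score rose in the first year may be more or less likely to stay, and this may differ by arm, since only intervention students at or above the 85th percentile are asked to attend 16 sessions. Year-1 values would allow a correction, and they are collected anyway. The binary H1a model is a separate matter.

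**Working it through.** **1. Reproduce the plan's count (Sample size and power analysis).** 120 × 0.36 = 43.2, about 43 per school; 43 × 0.65 = 27.95, about 28; 28 × 8 = 224, as stated. The stated detectable effect of 0.51 also reproduces: design effect 1 + 27 × 0.01 = 1.27; standard error √(2 × 1.27/112) = 0.151; with t on 6 df (8 schools minus 2) the result is 0.505, or 0.507 with the noncentral t.

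**2. Students affected.** 43 × 8 = 344 enrolled at or above the 85th percentile; 344 − 224 = 120 (35%) without year 2. At 1008 enrolled: 1008 × 0.36 = 363, of whom 363 × 0.35 = 127.

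**3. What these students contribute.** With only year 2 as response, and baseline and arm as predictors, the likelihood for a student with no year-2 value carries no information on the arm effect. The fit is a completers' ANCOVA with school clustering. Imputing year 2 from baseline and arm alone gives essentially the same answer.

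**4. Bias under assumed inputs.** The documents give no SD, no correlation between years and no dropout mechanism. Assumed: true effect −0.16 (the plan's target); SD 0.30 (back-solved from the stated 84% power with 6 df; a normal approximation gives 0.36); year-1/year-2 correlation given baseline 0.5 or 0.8; about 20–24% dropout between waves. Large-sample simulation, without clustering:

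| Dropout rises with year-1 gain (log-odds per SD) | Correlation | Completers' estimate |
|---|---|---|
| Intervention arm only, 0.8 | 0.8 | −0.196 |
| Intervention arm only, 0.8 | 0.5 | −0.183 |
| Intervention arm only, 0.4 | 0.8 | −0.179 |
| Intervention 0.8, comparison 0.4 | 0.8 | −0.177 |
| Both arms equally, 0.8 | 0.8 | −0.154 to −0.160 |
| Comparison arm only, 0.8 | 0.8 | −0.118 |
| Intervention arm only, opposite sign | 0.8 | −0.11 to −0.12 |

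The range in the equal-dependence row reflects whether gain is measured on a common scale or relative to the student's own arm. The joint model stays at about −0.16 throughout. In relative terms, −0.196 is 0.036/0.16 = 22% too large and −0.118 is 0.042/0.16 = 26% too small.

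**5. Precision.** With monotone loss, the student-level variance relative to completers is 0.65 × [ρ²/r₁ + (1 − ρ²)/0.65], where r₁ is the proportion retained at year 1 (assumed) and 0.65 the proportion at year 2.

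- r₁ = 0.825 (17.5% lost by year 1): 0.947, 0.896 and 0.828 for ρ = 0.5, 0.7 and 0.9, a reduction of 5%, 10% and 17%.
- r₁ = 0.70 (30% lost by year 1): 0.982, 0.965 and 0.942, a reduction of 2%, 4% and 6%.

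The student-level share of the variance of a school mean is (0.99/28)/(0.01 + 0.99/28) = 0.78. Including the school component, the reductions become about 4%, 8% and 13% in the first case and 1%, 3% and 5% in the second.

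**The case against.** The strongest reply is that the plan is under-specified rather than committed to a completers' analysis. It promises imputation and full information maximum likelihood, and it names Mplus among software able to handle missing data. Either technique, with year-1 values included, would retain these students. The response vector is never written out, and an outcome after two years with one equation per outcome is compatible with a longitudinal model that reports a year-2 contrast.

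Much of this stands. A reader might infer that the plan drops every student without a year-2 value, or that year-1 measurements go unused. The documents support neither: the first overlooks the two missing-data commitments, and the second treats silence as exclusion, although section V.i gives the year-1 data a purpose. The year-2 ANCOVA is the natural reading of the text, not an explicit statement.

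What does not stand is that the commitments settle the matter. The likelihood sentence refers back to the model just described, and the imputation sentence names no method or variables. Neither puts year-1 values anywhere.

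The bias is also fairly called scenario-dependent. No document shows dropout that differs by arm in its dependence on year-1 gain. The precision gain is modest as well, and smaller if loss comes early, which the reported higher-than-anticipated attrition before the first annual measurement makes plausible.

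**Conclusion.** The concern holds in this form: the model as most naturally read does not support the missing-data claim made for it, and the plan does not say that year-1 values enter the model, the likelihood or the imputation for H2 or H1b. Its missing-at-random claim then requires dropout to depend only on arm and the model covariates.

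With about 35% of students lacking year 2, the completers' estimate of a true −0.16 could lie between about −0.11 and −0.20 under the assumptions in step 4. The bias can go in either direction and nearly vanishes when dependence on year 1 is equal in both arms. The range illustrates and does not bound the bias, because the SD, correlation and dropout mechanism are all assumed. The gain in student-level variance is roughly 2–17%, so the main reason to act is protection against bias.

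A reader might also infer that the power statement is undermined. It is not: 224 already counts only students remaining after attrition, and no stated sample size or power figure is shown to be wrong.

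**What to change.** For each continuous H2 and H1b outcome, fit the year-1 and year-2 values jointly, with arm, wave, arm × wave, baseline value × wave, a random school effect and an unstructured within-student covariance. Name the year-2 arm contrast as the H2 or H1b estimate. The year-1 contrast then supplies the intermediate effects that section V.i mentions.

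An equally acceptable route, closer to the plan's own wording, is multilevel multiple imputation, done by arm and including year-1 values, followed by the year-2 model. Either way, state which missing-data method governs H2 and H1b and which variables enter it, before outcomes are analysed.

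The cost is analysis-plan wording and slightly more complex code, with no new data.
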